#### Randomization

In this study, patients will be randomized to G7 Acetabular System with CoC articulation and Taperloc Complete Microplasty stem or Exceed ABT Acetabular System with CoC articulation and Taperloc Complete Microplasty stem in 1:1 randomization scheme. The randomization will occur via a random number generator (manual or computer) by Sponsor using block randomization procedure (block size of 4). The doctor or other health care professional does not choose the participants for each group. For patients satisfying inclusion criteria, randomization will occur by retrieving the next randomly generated group assignment. Sites will control randomization assignment.

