## 2.2. NUMBER OF SITES AND SUBJECTS/PROCEDURES

This is a multi-center study to be conducted in Korea at a maximum of 4 sites

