### 3.2 EXCLUSION CRITERIA

Exclusion Criteria for this study should comply with the stated contraindications on package inserts of G7 Acetabular System, Exceed ABT Acetabular System, Ceramic on Ceramic bearing and Taperloc Complete Microplasty stem. These indications are stated below:

Absolute contraindications include: infection, sepsis, and osteomyelitis

Relative contraindications include:

- 1) uncooperative patient or patient with neurologic disorders who are incapable of following directions,
- 2) osteoporosis,
- 3) metabolic disorders which may impair bone formation,
- 4) osteomalacia,
- 5) distant foci of infections which may spread to the implant site,
- 6) rapid joint destruction, marked bone loss or bone resorption apparent on roentgenogram, and
- 7) vascular insufficiency, muscular atrophy, or neuromuscular disease.

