# Clinical Research Protocol

## 6. STATISTICAL ANALYSIS PLAN

### 6.1 SAMPLE SIZE CALCULATION

This is a multi-center, randomized controlled study to compare G7 Acetabular System /CoC articulation/Taperloc Complete Microplasty stem with Exceed ABT Acetabular System /CoC articulation/Taperloc Complete Microplasty stem. The primary endpoint is Harris Hip Score at 1 year postop. Study sample size is determined assuming the use of an independent, two-sided, two-sample pooled t-test for differences in mean Harris Hip Score.

Assumptions:

$\alpha = 0.05$	Probability of Type I Error
$\beta = 0.20$	Probability of Type II Error
$sd = 12$	Estimated standard deviation of the differences based on current Exceed ABT CoC study in Korea

Based on the assumptions above, a mean difference in Harris Hip Score of 5.8 points between groups can be detected with 68 cases in each group. If 15% dropout/lost to follow-up is assumed this will give n=80 in each group.

A total of 160 cases will be enrolled in the study.

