### 10.3. INFORMED CONSENT

Subjects (or the subject's legally authorized representative) will be provided with an informed consent and patient information sheet in order to give ample opportunity to review the consent and ask questions. The signed informed consent will be obtained before any study procedures begin. If the subject agrees to participate in the study, the subject/representative must sign the informed consent form. The witness and the Investigator must also sign the informed consent form. A copy of the informed consent form should be given to the subject/representative. All subjects who meet all of the entry criteria will be considered for inclusion in this trial. Any subject meeting any of the exclusion criteria will be excluded from the trial.

The informed consent form must be approved by the institution's IEC. Subjects will be informed of new information learned during the study, which may affect the subject's decision to continue participation in the study.

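### A printed fixed block size of 4, assignment controlled by sites and no stated step that hides the next assignment may leave upcoming cups predictable at entry

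*Combined protocol and SAP*

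**What the plan says.** The allocation procedure is one paragraph, headed Randomization, within section 6.1.

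- **Generation.** The Sponsor produces a 1:1 sequence with a manual or computer random number generator, "using block randomization procedure (block size of 4". One size is given, and it is printed in the protocol.
- **Release.** Once the inclusion criteria are met, "randomization will occur by retrieving the next randomly generated group assignment".
- **Control.** "Sites will control randomization assignment".
- **Stated safeguard.** "The doctor or other health care professional does not choose the participants for each group".

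Section 2.2 sets the number of centres: "This is a multi-center study to be conducted in Korea at a maximum of 4 sites". No section names sealed envelopes, a central telephone or web release, or a list holder separate from enrolment, and none says whether the list is common to all sites. Blinding appears only in section 7.3, in a general line on data systems that applies where there is any blinding.

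**The concern.** The operator knows which cup went into each earlier patient. If the enroller also knows that assignments come in balanced sets of four, some upcoming assignments can be deduced: the last of a set follows from the first three, and the last two follow if the first two match. If the site simply holds a readable list, nothing needs deducing.

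An enroller who can anticipate the next cup could, without breaking any written step, bring a patient forward, hold one back or judge eligibility differently. The groups could then differ in prognosis before surgery. The safeguard sentence states an intention and describes no mechanism to protect it. Checking eligibility before retrieval does not help if the next arm is already known or guessed when eligibility is judged.

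**Working it through.** **1. The plan's own figure.** Inputs from section 6.1: two-sided alpha 0.05, power 0.80, SD 12, difference 5.8.

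- n per group = 2 × (1.960 + 0.842)² × 12² / 5.8² = 67.2, rounded up to 68.
- 68 / (1 − 0.15) = 80 per group, 160 in total.
- With 68 per group the exact t-test detects 5.81 points.

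The sample size reproduces and is not in dispute. The plan gives no figure for predictability.

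**2. One list per site, all earlier site allocations known, block size known.** A 1:1 block of 4 has 6 equally likely orders, so 24 positions.

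- Certain in advance: the fourth position always (6), and the third when the first two match (2 of 6 orders). (6 + 2)/24 = 33.3%, or about 53 of 160.
- Best guess, by position: 1/2, 2/3, 2/3, 1. Mean = 17/24 = 70.8%, against 50% by chance.
- Always guessing the arm with fewer patients so far also gives 17/24, and needs no knowledge of the block size.

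**3. One concealed list shared by k equal sites, list position known.** Each earlier patient is seen with probability p = 1/k.

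- Certain: (p²/3 + p²)/4 = p²/3.
- Best guess, by position: 1/2; 1/2 + p/6; 1/2 + [1 − (1−p)²]/6; 1/2 + [1 − (1−p)³ − p³]/6 + p³/2. The mean of the four is g.

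| Sites sharing the list | Certain | Best guess | Best guess, position unknown |
|---|---|---|---|
| 2 | 8.3% | 59.9% | 58.7% |
| 3 | 3.7% | 56.9% | 56.5% |
| 4 | 2.1% | 55.4% | 55.2% |

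The last column is simulated (40 own patients, 4,000 runs). With position unknown nothing is certain, because unseen patients may always have completed the block. Two equal surgeons at one site who each know only their own cases match the two-site row (8.3%, 59.9%).

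**4. Readable list.** 100% known, whatever the block size.

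**5. Illustrative effect on 1-year HHS.** Two inputs are assumptions, not in the documents: steered patients differ by 2, 4 or 6 points, and one quarter of guesses are acted on, always in the same direction. Bias = difference × (2g − 1) × 0.25. The false-positive rate uses the noncentral t with SE = 12 × √(2/68) = 2.058 and 134 df.

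| Scenario | Bias (points) | False-positive rate |
|---|---|---|
| List shared by 4 sites, position known | 0.05, 0.11, 0.16 | 5.0% to 5.1% |
| One list per site | 0.2, 0.4, 0.6 | 5.1%, 5.5%, 6.1% |
| Readable list | 0.5, 1.0, 1.5 | 5.7%, 7.7%, 11.2% |

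**6. What changing the block size achieves with per-site lists** (simulated, 40 patients per site).

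- Size kept at 4 but withheld: a tracker who starts out thinking 4, 6 and 8 equally likely (an assumption) predicts about 17% of assignments with at least 95% probability, and about 29% of the last 20. Guessing stays near 71%.
- Sizes 4 and 6 varied at random: about 5.5% certain even if the set of sizes is known; guessing about 68.9%.

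**The case against.** Several objections have force.

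- **The highest deduced figures are not established.** The 33.3% and 70.8% need one list per site and full knowledge of earlier allocations. The protocol states neither. Sponsor generation with site control also fits Sponsor-made sealed envelopes opened at the site. This stands, so the figures are scenarios.
- **Some protection exists.** Section 10.3 already requires signed consent before any study procedure. The schedule in section 2.5.2 collects preoperative HHS and Oxford Hip Score, so part of any imbalance would show at baseline and could be adjusted for. This stands, but neither provision hides the next assignment, and unmeasured prognosis would not show.
- **Little motive is evident.** Both arms share the stem and the ceramic-on-ceramic bearing, and the amount of steering in the illustration is assumed. This stands, and it limits the likely size.
- **Database access is restricted.** Section 10.4 limits a doctor's view to his own patients. That covers data entry, not the allocation list, and surgeons know the cups they implant.

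Two stronger readings are tempting. A reader might infer from "Relative contraindications include" in section 3.2 that enrollers have discretion to steer. But those items are listed as exclusion criteria, and section 10.3 says "Any subject meeting any of the exclusion criteria will be excluded from the trial", so the text does not grant that discretion. A reader might also infer that the final analysis will be unadjusted and so cannot correct an imbalance. Section 6.1 says only "Study sample size is determined assuming the use of an independent, two-sided, two-sample pooled t-test"; section 6.3 names no model, so whether the analysis would adjust is unknown.

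**Conclusion.** The concern holds as a weakness in the stated procedure. A fixed block size is printed, control of assignment is given to the sites, and no step hides the next assignment, in a trial whose surgeons know the cup. It should be fixed because the remedy is cheap and concealment is the main defence at entry.

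Its size is uncertain. Predictability runs from 0% certain with about 55% guessing (a concealed list shared by 4 sites), through 33.3% and 70.8% (per-site lists, full history), to 100% (a readable list). Under the assumed steering, bias is 0.05 to 0.6 points in the scenarios without a readable list, and up to 1.5 points with one, against the 5.8 the trial is sized on.

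A reader might infer that a third of assignments were in fact known, that sites held an open list, or that selection took place. The documents support none of these: they leave the mechanism open and contain no evidence of bias.

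**What to change.** In the Randomization paragraph:

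1. Replace the sentence giving sites control. State that each assignment is released one patient at a time, after eligibility is recorded, either from a list held by the Sponsor or from Sponsor-prepared, sequentially numbered, opaque sealed envelopes. State that staff who enrol or operate have no access to the list. This rules out the 100% case and matters most.
2. State whether there is one list or one per site.
3. Move the block size to a document that sites do not hold. On its own this is only a partial reduction, because a site that tracks its past cups can learn a fixed size of 4.
4. If lists run by site, also vary the block size at random, for example 4 and 6. Certain assignments fall from 33.3% to about 5.5%, but guessing falls only from about 71% to about 69%.

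**Cost.** A few sentences of wording, and either a release step before surgery or about 160 envelopes; no added patients or visits. Varied blocks of 4 and 6 allow a within-site imbalance of up to 3 patients instead of 2.

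If enrolment is complete, report how assignments were actually held and released.

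### Blocks of 4 under site control at up to four sites, with no site term in the only comparison named for 1-year HHS: adding site to the primary model recovers a little power at almost no cost

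*Combined protocol and SAP*

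**What the plan says.** Section 2.2 describes a "multi-center study to be conducted in Korea at a maximum of 4 sites". The Randomization text in section 6.1 sets 1:1 allocation by a "block randomization procedure (block size of 4". The sponsor generates the sequence, the next assignment is taken as each eligible patient arrives, and "Sites will control randomization assignment". No stratification factor is named, and the text does not say whether there is one list for the trial or one per site.

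On the comparison itself, section 6.1 says: "Study sample size is determined assuming the use of an independent, two-sided, two-sample pooled t-test for differences in mean Harris Hip Score". This is the only between-arm test named for the primary endpoint, and it appears as the basis for the sample size. Section 6.3 lists the endpoints. The paragraph on primary and secondary endpoint analysis defines a population and invokes intention to treat. Neither names a test, a model, a covariate or a site term.

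**The concern.** When blocks run within site, each site contributes nearly equal numbers to both arms, so differences between sites largely cancel out of the arm difference. A pooled t-test still counts those differences as error. Its standard error is then too large, its intervals too wide and its test below the nominal level. If one list serves all sites, the arms need not balance within a site, and site differences add chance noise that a site term would remove.

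Sites could plausibly differ. Section 3.1 admits degenerative disease, rheumatoid arthritis, fracture and revision cases, and section 1.2 allows two surgical approaches. The trial looks for any difference between the systems (section 2.3) with 80% power, so precision available without extra patients is worth taking.

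**Working it through.** **Inputs from section 6.1.** Two-sided alpha 0.05, power 0.80, SD 12, difference 5.8 points, 68 evaluable per group, 15% dropout, 1:1 allocation, blocks of 4. From section 2.2: up to 4 sites.

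**Assumed.** The share r of HHS variance that lies between sites is not in the documents; I use 0, 5%, 10% and 20%. SD 12 is taken as the total between-patient SD, including site.

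**1. The plan's own figure.** n per group = 2 × (1.960 + 0.842)² × 12² / 5.8² = 2 × 7.849 × 144 / 33.64 = 67.2, rounded up to 68. The exact t-test gives 68.2, and power of 79.9% at 68. Then 68 / 0.85 = 80. Both stated figures reproduce.

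**2. Standard error with per-site blocks.** The pooled t-test reports about 12 × √(2/68) = 2.06 whatever r is. With site balanced out, the true standard error is 2.06 × √(1 − r): about 2.01, 1.95 and 1.84 at r = 5%, 10% and 20%.

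**3. Type I error with per-site blocks.** The approximation is 2 × [1 − Φ(1.96 / √(1 − r))]:
- r = 5%: cut-off 2.011, size 4.4%
- r = 10%: cut-off 2.066, size 3.9%
- r = 20%: cut-off 2.191, size 2.8%

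**4. Power with site in the model.** Replace SD 12 by 12 × √(1 − r) in the t-test at 68 per group. Power is 79.9%, 81.9%, 83.9% and 87.9% at r = 0, 5%, 10% and 20%. Put as sample size, 67.2 × (1 − r) gives 64, 61 and 54 per group for 80% power at the three non-zero shares, against 68.

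**5. Simulation.** 10,000 trials per setting, 136 patients at four sites (36, 36, 32, 32), blocks of 4. Monte Carlo standard error is about 0.2 points for size and 0.4 for power.

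| List | r | Size, no site term | Size, site term | Power, no site term | Power, site term |
|---|---|---|---|---|---|
| Per site | 0 | 5.0% | 5.0% | 80.1% | 80.2% |
| Per site | 5% | 4.7% | 5.2% | 80.3% | 81.6% |
| Per site | 10% | 4.0% | 5.2% | 81.8% | 84.5% |
| Per site | 20% | 2.7% | 4.8% | 81.9% | 87.6% |
| One shared | 0 | 5.0% | 5.0% | 80.3% | 79.2% |
| One shared | 5% | 4.9% | 4.8% | 79.9% | 81.3% |
| One shared | 10% | 5.4% | 5.4% | 80.1% | 83.2% |
| One shared | 20% | 4.9% | 4.7% | 79.9% | 87.4% |

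With per-site lists the unadjusted test falls below 5% as r grows. With one shared list it holds its level. The site term restores the level in the first case and gains power in both whenever r is above zero. At r = 0 it gains nothing, and under a shared list it costs about a point.

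**The case against.** The strongest reply is that the plan never commits to an unadjusted analysis. The t-test is stated only as the sample-size assumption, and section 6.3 specifies no primary test. That is correct: one cannot say the planned analysis is wrong, only that the sole comparison on record omits site and that nothing else has been specified.

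Second, a reader might infer that the reported standard errors necessarily fail to match the randomisation. The documents do not establish this. It needs per-site lists, which site control suggests but the text does not state, and it needs sites that differ in HHS. With one shared list, the t-test's standard error is correct. Site differences then enter only as chance imbalance, which that standard error already covers; they are not bias.

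Third, a reader might infer a false-positive risk or an underpowered trial. Neither follows. The error is conservative, and unadjusted power stays at about 80-82%.

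Fourth, the size of the gain rests on an unknown r, and the 20% case has no support in the documents. The analysed number is also uncertain, because section 6.2 carries forward missing scores and the count could approach 160 rather than 136. Both points stand and limit how firmly the magnitude can be stated.

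Finally, prescribing per-site lists could have a cost. With a known fixed block of 4 under site control, staff who know earlier assignments at their own site could deduce the last of a block. This stands, so the remedy should rest on the model term.

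**Conclusion.** The point holds as a low-cost improvement. The plan leaves open whether site is a stratum, and the only comparison it names for 1-year HHS ignores site. What is forgone is about 1 to 3 points of power at an assumed site share of 5-10%, about 6 to 7 points at 20%, and none at zero. If lists are per site, the unadjusted test would also run at about 4.5%, 4% or 3% instead of 5%. These figures assume 68 evaluable patients per group, four sites of similar size and SD 12 as the total SD. The stated sample size is sound, and nothing here shows a defective test or a shortfall from the planned 80%.

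**What to change.** In section 6.3, state that the primary comparison of 1-year HHS is a linear model with arm and site as fixed factors, reporting the adjusted arm difference with its 95% confidence interval. In section 6.1, state whether the blocked lists are separate by site. This records the scheme in use; it does not ask for a move to per-site lists.

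The cost is one sentence in each section and up to 3 degrees of freedom (number of sites minus one). If sites do not differ, the price is nil with per-site lists and about one point of power with a shared list. No extra patients are needed, and 80 per group can stay.

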### 6.2 HANDLING OF MISSING AND INCOMPLETE DATA

Attempt will be made to ensure that patients come back for scheduled follow-up evaluations. In case of missing data, for clinical outcome scores, Last Observation Carried Forward will be used to impute the missing data. For survivorship analysis, the data including implant in situ collected in the next follow-up will be used to calculate survivorship

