### 2.5.2. ASSESSMENT TIMELINES/SCHEDULE

Clinical and Radiographic Exams						
Data Collection item	Pre-operative	Intra-operative	Immediate Post-operative	6 Months	1 Year	2 years
Demographic and Medical History	X					
Operative Record		X				
Clinical Evaluation – OHS, HHS	X			X	X	X
Radiographic assessment			X	X	X	X
Squeaking, Dislocation			X	X	X	X
Adverse events including revisions			As required			

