### 6.3 DATA ANALYSES

The following analyses will be performed:

Primary endpoint is Harris Hip Score (HHS) at 1 year follow-up.

Secondary endpoints include

- Harris Hip Score at 2 years postop
- Oxford Hip Score at 6 months, 1 and 2 years postop
- Radiographic Assessment at Immediate post-op, 6 months, 1 and 2 years postop
- Incidence of squeaking at different follow-up visits
- Dislocation rate at different follow-up visits
- Survivorship

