# Clinical Research Protocol

## Primary and Secondary Endpoint Analysis

Analysis for primary and secondary endpoints will use patient population which consists of those cases with complete data for one or more of the primary and secondary endpoints. Analysis is based on intention to treat principle.

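### Last observation carried forward is not limited to post-operative scores, so a pre-surgery HHS or OHS can be analysed as an outcome, and no sensitivity analysis would show it

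*Combined protocol and SAP*

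**What the plan says.** Section 6.3 sets the primary endpoint: "Primary endpoint is Harris Hip Score (HHS) at 1 year follow-up". Among the secondary endpoints it lists "Oxford Hip Score at 6 months, 1 and 2 years postop" and "Radiographic Assessment at Immediate post-op, 6 months, 1 and 2 years postop".

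The schedule in section 2.5.2 has a row "Clinical Evaluation – OHS, HHS", marked pre-operatively and at 6 months, 1 year and 2 years. No score is scheduled between surgery and 6 months.

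For missing scores, section 6.2 says only that "for clinical outcome scores, Last Observation Carried Forward will be used to impute the missing data". It sets no limit on which earlier observation may be carried, and no alternative or sensitivity analysis appears anywhere.

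The paragraph on Primary and Secondary Endpoint Analysis defines the population as "those cases with complete data for one or more of the primary and secondary endpoints", under intention to treat. Section 6.1 plans for 68 evaluable cases per group and adds: "If 15% dropout/lost to follow-up is assumed this will give n=80 in each group".

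**The concern.** A pre-operative score is not an outcome of the operation. Read with the schedule, section 6.2 allows one to be used as such in two ways.

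- **HHS at 1 year (primary).** This needs two missed visits, 6 months and 1 year. The last observation is then the pre-operative HHS. A patient who misses only the 1-year visit has the 6-month score treated as an observed 1-year value, even if a 2-year score exists.
- **OHS at 6 months (secondary).** One missed visit is enough, because the only earlier scheduled score is pre-operative.

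The population definition does not settle whether such patients are analysed. Taken across endpoints, "cases with complete data for one or more of the primary and secondary endpoints" could be met by the immediate post-operative radiograph alone, which brings them in. Taken endpoint by endpoint, it leaves them out.

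If HHS rises after surgery, each pre-operative value carried forward dilutes a true difference and inflates the SD beyond the planned 12. If one arm has more such values than the other, its mean is pulled down and nothing in the plan would reveal it.

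**Working it through.** **Inputs from section 6.1.** Two-sided pooled t-test, alpha 0.05, beta 0.20, SD 12, difference 5.8, 68 evaluable and 80 enrolled per group.

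**The plan's own figure.** n = 2 × (1.960 + 0.842)² × 12² / 5.8² = 67.2, so 68 per group; 68 / 0.85 = 80. Both reproduce. Noncentral-t power is 79.9% at 68 per arm and 86.0% at 80. The planned loss is 80 − 68 = 12 per arm. Section 6.1 therefore counts lost patients as contributing nothing, whereas section 6.2 can put them back with imputed scores.

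**Assumptions, because the documents give no figures.** The gap G between pre-operative and 1-year HHS is 20, 30, 40 or 50 points (G in one arm, G + 5.8 in the other, with equal pre-operative means). The pre-operative SD is 12. Eighty per arm are analysed, of whom k per arm carry a pre-operative score; k cannot exceed 12 if loss is as planned. Other carried scores are 6-month scores assumed to show the full effect.

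**Formula for k carries in each arm**, with f = k/80:

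- mean difference = (1 − f) × 5.8
- expected pooled variance = 144 + (80/79) × f(1 − f) × [G² + (G + 5.8)²]/2
- with k fixed, the true standard error of the difference stays at 12 × √(2/80) = 1.897, while the t-test uses the inflated SD

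Example, k = 4 and G = 30: f = 0.05. The difference is 0.95 × 5.8 = 5.51. The variance is 144 + 1.0127 × 0.0475 × (900 + 1281.6)/2 = 196.5, so the SD is 14.0. The difference needed for significance is 1.975 × 14.0 × √(2/80) = 4.38. Then z = (4.38 − 5.51)/1.897 = −0.60, and power is about 72.5%.

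Simulation (100,000 trials per setting) agrees with this approximation:

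| Carries per arm (fixed) | G=20 | G=30 | G=40 | G=50 | Same patients left out |
|---|---|---|---|---|---|
| 0 | 86.0% | 86.0% | 86.0% | 86.0% | – |
| 1 | 84.0% | 82.8% | 81.3% | 79.1% | 85.5% |
| 2 | 82.0% | 79.6% | 76.0% | 71.9% | 85.1% |
| 3 | 79.7% | 76.1% | 70.7% | 64.1% | – |
| 4 | 77.5% | 72.5% | 65.1% | 56.2% | 84.1% |
| 12 (worst case) | 57.6% | 43.4% | 27.1% | 13.8% | 79.9% |

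The last column is noncentral-t power at 80 − k per arm. Power reaches or falls below 80% at about 3 to 4, 2, 2 and 1 carries per arm; 3 carries at G = 20 (79.7%) and 2 at G = 30 (79.6%) are practically on the line. A pre-operative SD of 8 or 16 moves these crossings by at most one carry.

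**Random counts.** If the number of carries varies by chance around k, power is 83.4/81.8/79.4/76.9% at an expected 1, 80.9/77.5/73.4/68.6% at 2 and 78.2/73.5/67.6/61.5% at 3. At an expected 12 it is about 57/45/36/28%, so the 13.8% above depends on exactly 12 in each arm.

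**No true difference.** With 4 carries in each arm the test rejects 3.7/2.6/1.5/0.8% of the time with fixed counts and about 5% with random counts, so equal loss creates no false positives. Each extra carry in one arm shifts its mean by G/80 = 0.25/0.38/0.50/0.63 points. Illustratively, 4 against 8 carries gives a false difference of 4G/80 = 1.0/1.5/2.0/2.5 points. Rejection is then 5.7/6.0/6.1/5.4% with fixed counts and 7.6/9.9/12.1/13.9% with random counts.

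**The case against.** The strongest reply is that the plan nowhere says a pre-operative score will be analysed as an outcome. For the primary endpoint this takes two missed visits, a carry reaching back before surgery, and the broad reading of the population definition. The 15% allowance could equally mean that lost patients are left out. Section 3.3.1 also requires a final evaluation form at withdrawal, which might supply a later score. The size of the effect rests on two undocumented inputs and runs from mild (84% at one carry and G = 20) to severe. The 4 against 8 imbalance is hypothetical. One sentence would cure the core problem; a new model is a preference.

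Much of this limits the size but does not remove the point. The two-visit condition is real and narrows the primary-endpoint case; it does not apply to 6-month OHS. The final form is not said to include HHS or OHS, and section 3.4 counts failure to return as a withdrawal reason, so such a patient may never be scored. If only post-operative carries were intended, 6-month OHS has no scheduled score to carry, and the plan should say what happens then. The unequal-loss figures are illustrations only: the documents give no reason to expect imbalance. One sentence is indeed the minimum; the model is recommended because it also deals with 6-month scores standing as 1-year values.

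**Conclusion.** The point holds and should be fixed. As written, section 6.2 lets a pre-operative score stand as a post-operative outcome: after one missed visit for 6-month OHS, and after two for the 1-year primary HHS. Nothing in the document clearly bars this, and no sensitivity analysis would expose it.

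The main consequence is loss of power. Under the stated assumptions, somewhere between one and four pre-operative carries per arm, out of 12 planned losses, brings power to about 80% or below. In every setting calculated, carrying the pre-operative score does worse than omitting the patient. With equal loss and timing the null comparison is not biased; bias needs more pre-operative carries in one arm. Confidence in the size is medium, because the gap and the number of carries are assumed. The sample size arithmetic itself is sound.

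**What to change.** **Minimum.** Add one sentence to section 6.2 stating that a pre-operative score is never used as a post-operative outcome, and say how a missing 6-month OHS is then handled.

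**Preferred.**

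- In section 6.2, replace carry-forward for HHS and OHS with a likelihood-based repeated-measures model (MMRM) on the scheduled post-operative scores. Include treatment, visit, treatment by visit, baseline score and site, with the 1-year HHS contrast as primary. The pre-operative score becomes a covariate, 6-month scores no longer pass as observed 1-year values, and 2-year scores are used where they exist.
- Add one missing-not-at-random sensitivity analysis, for example delta-adjusted multiple imputation.
- In the Primary and Secondary Endpoint Analysis paragraph, define the analysis set as all randomised patients as assigned, using all available post-operative scores.

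**Cost.** SAP wording and modest programming; no new patients, visits or data, and 80 per group can stand. The model assumes data are missing at random, and patients with no post-operative score contribute nothing to it. The sensitivity analysis is there to examine both limits.
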